1. ADMINISTRATIVE INFORMATION

1.1. Trial registration

This trial will be registered with the relevant clinical trial registries upon ethical approval and before the start of the trial intervention.

1.3. Expected duration of study

Recruitment: 2 months

Intervention and follow period for participants: 12 months

1.5. Stakeholder involvement

The Royal Children's Hospital (RCH) Cystic Fibrosis (CF) team have worked alongside the following stakeholders in the creation of the following protocol:

- RCH Virtual Care team
- RCH electronic medical record (EMR) team
- Five parents of children with CF, currently being cared for at RCH
- Melbourne Academic Centre for Health
- RCH Health Services Research Unit

Collaboration on prototypes of the remote monitoring system have been trialled and improved upon by the above teams over the past 18 months prior to the ethics application being submitted. Consumers were also involved in guiding the pilot protocol and plans for intervention.

2. INTRODUCTION AND BACKGROUND

2.1. Trial rationale and aim

The aim of this study is to assess the feasibility, acceptability, and potential effectiveness of a new model of care involving remote symptom monitoring and automated treatment plans in children with Cystic Fibrosis who are on highly effective modulators.

2.2. Background

Cystic Fibrosis (CF) is the most common genetically inherited life limiting disease caused by a defect on chromosome seven affecting the cystic fibrosis transmembrane conductance regulator (*CFTR*) gene[1]. The *CFTR* gene encodes for an ion channel (also called CFTR) which helps regulate the movement of salt and water across the cell surface. The defect in the CFTR channel leads to dehydration of the cell surface liquid and the stagnation of movement of mucus which lines the cell surface. CF is a multisystem disease but primary manifestation is in the lungs, with decreased movement of mucus in the lungs leading to a recurrent cycle of infection and inflammation resulting in irreversible damage with respiratory failure being the most common cause of death[1]. Pulmonary exacerbations result in loss of lung function and in turn decreased life expectancy[2]. It is known that in approximately 25% of exacerbations people with CF do not return to their baseline lung function[3, 4]. It is proposed that delayed identification and treatment of pulmonary exacerbations may contribute to worse outcomes for people with CF. Several studies have found that those CF centres who review their patients more frequently and treat exacerbations more aggressively have better outcomes[5, 6].

Recently there have been advancements in the medical management of people with CF, with the introduction of new drugs targeting the effectiveness of CFTR channel. Collectively these drugs are called CFTR modulators, and they increase the cell surface liquid to varying effects improving outcomes for people with CF[7]. Two drugs have been deemed “highly effective modulators” in the CF literature, due to the significant improvements in outcomes seen in their associated trials. elexacaftor/tezacaftor/ivacaftor (ETI) and ivacaftor are the two highly effective modulators known to improve forced expiration volume in the first second (FEV_1), a measure of lung function, by over 10% and decreased pulmonary exacerbations by 35-63%[8-13]. These two drugs are available to approximately 90% of the CF population, with ivacaftor being approved by the Therapeutic Goods Association in 2014[14] and ETI being approved in March of 2022[15]. Currently much is unknown about both the short and long term impacts of highly effective modulators on symptoms exhibited during a pulmonary exacerbation. It is unclear how the improved health of people treated with highly effective modulators will impact on pulmonary exacerbation detection. For example, if modulator treatment result in milder symptoms during a pulmonary exacerbation, they may go undetected in the current care model which relies on patients and families recognising the symptoms.

Alongside these medical advancements in the care of people with CF, the COVID 19 pandemic led to a significant expansion in the utilisation of remote monitoring and virtual clinics. Prior to 2020 there

Study Name: Acceptability, feasibility and impacts of remote symptom monitoring and automated treatment plans in children with Cystic Fibrosis (CF) on highly effective modulators: a pilot randomised controlled trial.

Protocol Number: 91117

Version & date: version 2, 28.10.2022

was limited literature relating to the use of remote monitoring or telehealth clinics in people with CF[16-25]. A multi-centre RCT from the United States, reported an increase in the number of pulmonary exacerbations detected in a home monitoring group compared to usual care, however this did not impact clinical outcomes in the trial period[18]. A more recent study demonstrated good participant engagement in their remote monitoring trial, however exhibited a large drop off rates in participant interaction with the remote symptom monitoring model as the study progressed [26]. Studies assessing symptoms remotely all required interactions between the participants and CF teams to implement treatments to any pulmonary exacerbations detected by the remote monitoring. Since this time, there have been vast technological enhancements to virtual platforms, app integration, remote monitoring through wearables and other devices, however integration into everyday care in CF remains limited.

The RCH CF service is limited by our current model of care which affords four clinic visits per patient per year. This means most children with CF get their symptoms monitored four times a year in clinic, leaving large gaps of time without assessment which may lead to unidentified and untreated exacerbations affecting their long-term outcomes. The current model of care also places a large burden on parents and carers of children with CF to monitor their child's symptoms between clinic appointments. The RCH CF team has worked hard to sign up 80% of its population to the RCH Patient portal and has gained access to home spirometers for most children over the age of 5 years, setting up the service to implement more remote monitoring.

Evidence gap

Currently there is no literature relating to remote symptom monitoring in the era of highly effective modulators in people with CF. It is unknown whether or not the significant improvements in clinical outcomes translate to changes in symptom presentations associated with pulmonary exacerbations. It is unknown whether remote monitoring will have the required sensitivity to detect pulmonary exacerbations in this new era.

Whilst remote monitoring and telehealth models of care have shown varying rates of feasibility and effectiveness, all previous studies have required the CF multidisciplinary teams (MDT) input to prescribe patients with treatment plans in the face of a pulmonary exacerbation. There is no known literature relating to implementation of automated treatment plans in people with CF.

This study will generate new evidence relating to the use of remote symptom monitoring and automated treatment plans in children with CF on highly effective modulators. To do so we will compare this new model of care to usual care in a pilot randomised controlled trial.

3 TRIAL OBJECTIVES AND OUTCOMES

3.1 Aims

In a sample of children with CF attending the RCH CF service and on a highly effective modulator, we aim to:

- evaluate the feasibility and acceptability of a remote symptom monitoring and automated treatment plan care model (intervention only)
- understand changes in outcome measures over time between the two groups in children on highly effective modulators; and

Study Name: Acceptability, feasibility and impacts of remote symptom monitoring and automated treatment plans in children with Cystic Fibrosis (CF) on highly effective modulators: a pilot randomised controlled trial.

Protocol Number: 91117

Version & date: version 2, 28.10.2022

- determine the costs to the healthcare system and to families of the remote symptom monitoring and automated treatment plan care model versus usual care.

Hypothesis:

We hypothesise that compared with usual care, the remote symptom monitoring and automated treatment plan care model will:

1. Be an acceptable method of monitoring for families and the CF MDT;
2. Be a feasible method of monitoring for families and CF MDT;
3. Detect more pulmonary exacerbations earlier and enable earlier treatment than usual care; and
4. Be cost neutral compared to usual care.

Objectives:

Primary:

1. To assess the **uptake and feasibility** of the remote monitoring and automated treatment plans (measured as number of symptom surveys completed, and tasks completed);
2. To assess the **impact and acceptability** of the remote system monitoring and automated treatment plans on **family experience** (measured as experience of the program; acceptability of the program);
3. To assess the **impact and acceptability** of the remote system monitoring and automated treatment plans on **CF MDT experience** (measured as experience of the program; acceptability of the program) compared to usual care.

Secondary:

4. To understand **changes in outcome measures** over time between the two groups in children on highly effective modulators
5. To assess the **cost-effectiveness** of the remote monitoring and automated treatment plans compared to usual care by undertaking a health economic evaluation from healthcare and societal (family) perspectives.

Primary and Secondary Objectives	Outcome of Interest	Data Sources	Methods of collection	Period of Data Collection		
				3/12	6/12	12/12
ACCEPTABILITY & FEASIBILITY						
1. What is the feasibility of the remote monitoring system for families and CF MDT ?	What is the uptake of the remote monitoring and automated treatment plans (number of surveys completed, number of tasks completed, number of contacts between CF MDT and patients)	EPIC EMR	EPIC pre-made reports specific to the trial.	●	●	●
2. What is the CF MDT's experience of the remote monitoring system?	Confidence in system detecting exacerbation, appropriateness treatment initiated, confidence in navigating system and data in EPIC, feasibility/acceptability of the model	MDT semi structured interviews	Qualitative interviews completed via MS Teams	●		●
3. What is the families experience of the remote monitoring system?	Confidence in system detecting exacerbation, appropriateness treatment initiated, confidence in navigating the portal, feasibility/acceptability of the model	Family semi structured interviews	Qualitative interviews completed via MS Teams	●		●
CLINICAL EFFECTIVENESS						
4. What is the impact of remote monitoring on changes in outcome measures over time?	Number of pulmonary exacerbations detected, change in lung function, outpatient clinic visits, hospital admissions and length of stay, antibiotic usage and QOL scores	Trial data from EPIC Family Survey CFQ-R EQ-5D-Y	Chart review and EPIC reports, exacerbation survey & QOL surveys via REDCap	●	●	●
HEALTH ECONOMIC EVALUATION						
5. What is the cost of implementing the model of care? What is the cost effectiveness ?	Costs of conducting the model of care compared to usual care; costs/savings of change in OP/admissions encounters; costs/savings to families compared with accessing usual care.	Trial data and supplementary unit costings	Trial data on the model of care, health service costs, health service use and patient costs and outcomes will be combined with relevant unit costs to produce a cost-effectiveness analysis.	●	●	●

Study Name: Acceptability, feasibility and impacts of remote symptom monitoring and automated treatment plans in children with Cystic Fibrosis (CF) on highly effective modulators: a pilot randomised controlled trial.

Protocol Number: 91117

Version & date: version 2, 28.10.2022

TRIAL DESIGN Overall design**Design:**

This will be a pilot randomised, non-blinded, single center trial in children with CF attending the RCH on highly effective modulators. The study will compare usual care to an intervention arm, with the intervention being the new remote symptom monitoring and automated treatment plan model of care.

Participants:

Participants will be children with a confirmed diagnosis of Cystic Fibrosis under the care of RCH, on a highly effective modulator (ETI or ivacaftor) and their caregiver. Participants will be included in the study only if they meet all of the inclusion criteria and none of the exclusion criteria.

Inclusion criteria:

- Diagnosis of Cystic Fibrosis
- On ETI or ivacaftor for a minimum of 2 weeks
- Clinically stable without antibiotic treatment for a pulmonary exacerbation in 2 weeks prior to consent
- Attending RCH CF clinic
- Able to complete home spirometry (standard of care for all children with CF >5 years at RCH CF clinic)
- Sufficient English to complete a survey
- Access to a smart phone to access remote symptom monitoring surveys

Exclusion criteria:

- Participants not signed up or not willing to sign up to the RCH Portal (note that 80% of RCH CF patients are already signed up to the portal)
- Participants who do not have access to a smartphone or computer on a daily basis
- Participants who do not have access to a home spirometer for lung function purposes
- Participants will be excluded from the study for technological access reasons such as lack of access to the RCH Portal and IT equipment as this is the basis of the intervention.

Sample:

Although this is a randomised controlled trial it is a pilot and currently there is no known sample size in the literature relating to a pilot trial. However, we will aim to include a minimum of 30 participants in the study in line with other pilot trials conducted by CI [name] [27]. We believe this will give us sufficient data on the feasibility and acceptability of the new model of care and potential effectiveness. If the intervention is feasible and acceptable the outcome data, which can be collected with minimal burden on participants and resources, will be crucial to inform sample size calculations for fully powered RCTs.

Study Name: Acceptability, feasibility and impacts of remote symptom monitoring and automated treatment plans in children with Cystic Fibrosis (CF) on highly effective modulators: a pilot randomised controlled trial.

Protocol Number: 91117

Version & date: version 2, 28.10.2022

Recruitment:

Potential participants will be recruited through the following multi-pronged approach:

Patients

- *Self-enrolment:*

Participants will be sent information regarding the study, including study overview and contact details for the study team, in a letter signed by the CF centre director via the RCH Portal (Appendix 1). The letter will include a QR code taking interested families directly to a screening questionnaire for study eligibility (Appendix 2). If meeting eligibility criteria the participant will be linked to the PICF (Appendix 3) where they can read in more detail about the study. There will also be a child information sheet regarding the study. Families will indicate consent by checking a box at the start of the online survey and will subsequently be recruited into the study. Families will then complete the baseline demographic survey (Appendix 4). The initial demographic survey will include an item seeking their permission to contact them to potentially participate in a qualitative interview via MS Teams if allocated to the intervention arm. These families will be invited to include a preferred contact mode (either email or telephone) and a member of the research team will contact parents or carers via their preferred contact mode to invite them to participate in the interview.

- *Phone call enrolment:*

For those who do not self-enrol from the initial letter, a follow up phone call will be made by the principal investigator (an RCH CF physiotherapist) one week after letter has been sent out, to ascertain interest in the study. The principal investigator will explain the study to the potential participant. Interested families will complete the screening survey (Appendix 2) over the phone with the PI and will be sent links to the: 1) PICF (Appendix 3), 2) Online consent, and 3) Baseline demographic survey (Appendix 4) by the RCH portal.

- *Clinic enrolment (face to face or via telehealth):*

Potential participants attending their routine CF clinic may be approached by the principal investigator to ascertain their interest in the study. The principal investigator will explain the study to the potential participant. Interested families will complete the: 1) screening survey (Appendix 2) 2) PICF (Appendix 3), 3) consent, and 4) Baseline demographic survey (Appendix 4) in person or if time does not permit will be sent links by the RCH portal.

Recruitment will begin in December of 2022 and continue until February 2023 or until minimum sample size is achieved.

There are currently 100 children on either ETI or ivacaftor who are signed up to the RCH patient portal, showing that recruitment to this study is feasible.

CF MDT

Study Name: Acceptability, feasibility and impacts of remote symptom monitoring and automated treatment plans in children with Cystic Fibrosis (CF) on highly effective modulators: a pilot randomised controlled trial.

Protocol Number: 91117

Version & date: version 2, 28.10.2022

All members of the CF MDT will be invited to participate in semi structured interviews (Appendix 6) via email as part of the acceptability and feasibility evaluation.

Consent:

Parents

In the initial explanatory letter sent to participants a link a brief inclusion/exclusion survey will be included. If participants meet these criteria, they will be directed to the Participant Information and Consent Form (PICF) (Appendix 3). This document will describe the purpose of the trial, the procedures to be followed, and the risks and benefits of participation – as per the initial letter sent to them. It will be made clear that all participants will be free to withdraw from the study at any time without jeopardizing their medical care. Informed consent will be obtained from the parent/caregiver prior to baseline demographic survey commencement.

Children with CF

For all consent approaches age appropriate written and/or oral information will be provided to the child/adolescent in accordance with their level of maturity (where appropriate). The investigator will provide the Parent/Guardian Information and Consent Form to the parent/legal guardian and, the Participant Information and Consent Form to the child/adolescent. Both of these documents are listed in Appendix 5 This document will describe the purpose of the study, the procedures to be followed, and the risks and benefits of participation.

The parent/legal guardian will be invited to provide written consent. Where deemed competent and mature to provide consent, the child/adolescent will also be invited to provide written consent. The level of maturity will be determined by the Investigator in accordance with local process. Consent will be voluntary and free from coercion.

CF MDT staff

CF MDT will be sent a PICF (Appendix 6) describing the purpose of the trial and inviting them to participate in semi-structured interviews. Once consent has been gained, the PI will contact them to make a time for the semi-structured interview.

Randomisation:

Randomisation will occur after consent in signed and will be performed by a person independent to the study. A stratified randomization will be employed with the goal of ensuring balance between study arms by risk category employed by the RCH CF team. The randomisation schedule will be created by computer-generated random numbers, before the first participant has been recruited. The participant cohort will be stratified by child risk category (2 levels of category: 1 Very high risk & high risk and 2 Medium risk & low risk). Within each strata, permuted block randomisation will be used to ensure balance between the intervention and control group. A randomly generated sequence of block sizes containing 2, 4, or 6 participants will be used. This will help ensure balance in numbers between intervention and control groups, prevent potential confounders of risk category type impacting the measurement of outcomes, and prevent any predictability in intervention allocation[28]. The schedule will be held by an independent person, and allocation will not be

revealed prematurely to CI. Because of these procedures, the research team will be unable to predict which group the participant will be allocated to.

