4 STUDY VISITS AND PROCEDURES

Study timeline:

Information relating to study sent via letter		
Opportunity for self-enrolment, clinic enrolment, phone enrolment		A
Consent		B
Randomisation	Intervention	Control
Baseline data collection	C D E	C D E
3 months	F G H	F G
6 months	F G	F G
12 months	D E F G H	D E F G
A	Survey screening for inclusion/exclusion criteria sent to all potential participants	
B	Children meeting inclusion criteria and interested in study referred to PICF and consent form	
C	Demographic information (as part of the baseline questionnaire)	
D	Spirometry	
E	CFQ-R & EQ-5D-Y (as part of the baseline questionnaire)	
F	Data download from EPIC (admissions, LOS, contacts with CF team)	
G	Online follow up questionnaire	
H	Semi structured interviews	

Description of intervention

Remote symptom monitoring and automated treatment plans:

Participants randomised to the intervention arm will receive onboarding material (Appendix 7) detailing instructions of how to access and use the remote monitoring system via the RCH portal.

Participants will be asked to complete two surveys:

1. Baseline symptom survey (Appendix 8)

Participants will be prompted to complete survey by a push notification sent to their mobile phone and built into EPIC at the:

- Commencement of the trial;
- Each month post commencement of the trial; and
- After each exacerbation is detected.

2. Twice weekly symptom survey (Appendix 8)

Participants will be prompted to complete a survey by a push notification sent to their mobile phone and built into EPIC twice a week

The survey is a validated tool for detecting pulmonary exacerbations in people with CF[29].

A score is assigned to each survey field. Every symptom-monitoring questionnaire completed by the patient or patient's family is compared to their last known baseline questionnaire.

If the frequency or severity of **two or more symptoms** have worsened compared to baseline, the **Exacerbation Pathway** is triggered (Appendix 9 for exacerbation calculations).

If the system detects an exacerbation, it will send an automated treatment plan out to the patient and their caregiver including:

- Directions to commence a specific antibiotic
- Directions to change/or increase airway clearance and inhalation therapy.

Information regarding antibiotic, airway clearance and inhalation therapy prescription will be extracted from the participant's EPIC file.

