Participants in the control arm will receive usual which consists of quarterly CF clinic visits and more urgent visits triggered by telephone calls from families concerned about their child's clinical status. This model of care relies on the participant/caregiver contacting the CF team if they notice a change in their symptoms.

Questionnaires

All online questionnaire links will be sent to participants via the portal.

Screening questionnaire:

A once off screening questionnaire will be linked to the initial study letter for participants to fill out prior to accessing the PICF and consent forms (Appendix 2).

Baseline:

Demographic questionnaire and data collection

A baseline demographic survey will be sent to all participants after online consent is gained (Appendix 4). Patient demographic and baseline data will also be collected via the EMR (Appendix 11)

Cystic Fibrosis Questionnaire- R (CFQ-R)

The CFQ-R (Appendix 12) is a validated questionnaire used to assess the health-related quality of life of people with CF of all ages [30]. It contains five generic domains, four specific domains, three

symptom scales and an overall health perception scale. It takes approximately 10 minutes to complete and can be self-administered.

EQ-5D-Y

The EQ-5D-Y (Appendix 13) is a validated survey assessing quality of life in a range of populations including CF [31]. It is a five-dimension survey encompassing mobility, looking after myself, doing usual activities, having pain or discomfort and feeling worried, sad or unhappy. It takes approximately 3 minutes to complete

3, 6 & 12 month follow up survey

A follow up survey will be sent to both the intervention and control group at 3, 6 and 12 months and will ask about number of pulmonary exacerbations, and data for health economics evaluation (e.g. time off work, travel costs) and information relating to burden of trial (Appendix 10)

At 12 months the *CFQ-R* and *EQ-5D-Y* will be completed also.

Procedures:

Spirometry

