- Increased burden of care to families by having to fill out the symptom surveys twice a week
 - Patient choice to fill out survey
- Increased workload for CF team without extra funding
 - Mostly automated system, relieving large burden on CF team
 - CF team involved in design of the intervention

6 Analysis:

STATISTICAL METHODS

Methods of analysis

Quantitative analysis:

Statistical analysis will be performed utilizing Statistical Package for the Social Sciences (SPSS). Descriptive statistics will be presented as mean (standard deviation, SD) or median (interquartile range, IQR). Categorical variables will be reported descriptively using frequency (n) and proportion (%).

Primary analysis:

1. To assess the **uptake and feasibility** of the remote monitoring and automated treatment plans
 - a. Total number of symptom surveys completed will be compared to total number of surveys expected and presented as a percentage.
 - b. Total number of tasks completed will be compared to expected number of tasks completed and presented as a percentage.
 - c. Number of contacts between CF team and family will be collated and compared between the intervention and control group using paired t tests or the non-parametric equivalents.

Secondary:

1. To understand **changes in outcome measures** over time between the two groups in children on highly effective modulators
 - Number of exacerbations detected
 - Total number of exacerbations per year will be calculated in each arm and presented descriptively. Comparison between groups will occur using t-tests or Chi squared test (or non-parametric alternatives as required)
 - Change in FEV₁
 - Data will be expressed as litres and percentage predicted. For each individual the FEV₁ at study entry will be compared to the FEV₁ at study completion, to determine the change in FEV₁. The average change in FEV₁ between the intervention and control group will then be compared using t-tests or Chi squared test (or non-parametric alternatives as required).
 - Number of admissions
 - Total number of admissions per year will be calculated in each arm and presented descriptively. Comparison between groups will occur using t-tests or Chi squared test (or non-parametric alternatives as required)
 - Hospital length of stay
 - Total number of hospital days per year will be calculated in each arm and presented descriptively. Comparison between groups will occur using t-tests or Chi squared test (or non-parametric alternatives as required)

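### Lung function and quality of life are marked at 3, 6 and 12 months in the objectives table but scheduled only at baseline and 12 months, and FEV1 change is compared without baseline adjustment

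*Protocol*

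**What the plan says.** Four places in the Protocol bear on this.

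- **Section 3.1, objectives table, row 4 (clinical effectiveness).** The outcomes are "Number of pulmonary exacerbations detected, change in lung function, outpatient clinic visits, hospital admissions and length of stay", followed by antibiotic use and quality-of-life scores. Under the column heading "Period of Data Collection" the row is marked at 3, 6 and 12 months. The table has no baseline column.
- **Section 4, study timeline.** Spirometry is item D, and CFQ-R with EQ-5D-Y is item E. Both appear at baseline and 12 months in each arm and at no other visit. The 3- and 6-month entries are items F and G, plus interviews in the intervention arm at 3 months. Item F is "Data download from EPIC (admissions, LOS, contacts with CF team"; spirometry is not in its list.
- **Section 4, Questionnaires.** The follow-up survey goes out at 3, 6 and 12 months, but the two quality-of-life instruments are repeated at 12 months only.
- **Section 6, Secondary, Change in FEV1.** "For each individual the FEV₁ at study entry will be compared to the FEV₁ at study completion, to determine the change in FEV₁". Then: "The average change in FEV₁ between the intervention and control group will then be compared using t-tests or Chi squared test", or a non-parametric alternative. No adjustment for baseline or for the randomisation stratum is mentioned.

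Two further statements matter for the remedy. Usual care consists of "quarterly CF clinic visits" plus urgent visits, and the intervention arm keeps the quarterly visits. The intervention arm alone also has lung function measured when the system detects an exacerbation and again 10 to 14 days later.

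**The concern.** Staff working from the objectives table would look for FEV1 and quality-of-life data at 3 and 6 months. Staff working from the timeline would not. The table names chart review and EPIC reports as a method of collection, but no rule says which FEV1 values count. Someone filling the 3- and 6-month cells from the chart could therefore pick up exacerbation-triggered tests, which exist by design in one arm only.

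For quality of life, the economic evaluation in section 6 uses an area-under-the-curve method. With two measurements that area is a straight line between baseline and 12 months, so which schedule applies affects the result.

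The analysis raises a second issue. With about 15 children per arm, an unadjusted change score is not the most precise use of a baseline that is already collected. It also gives no value for a child without a 12-month measurement. The Protocol says the outcome data will inform sample sizes for later trials, so precision and a clear definition have some value even without a power claim.

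**Working it through.** **1. The passages side by side**

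| Place | FEV1 | CFQ-R and EQ-5D-Y |
|---|---|---|
| Objectives table, row 4 | 3, 6, 12 months | 3, 6, 12 months |
| Study timeline | baseline, 12 months | baseline, 12 months |
| Questionnaires text | not covered | baseline, 12 months |
| Section 6 | entry and completion | no time points given |

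The timeline, questionnaire text and FEV1 analysis agree with one another. The objectives table is the outlier, for both outcomes.

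**2. Inputs for the precision check**

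The Protocol gives no SD, correlation, effect size or power, so there is no figure of its own to reproduce. Assumptions:

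- 15 per arm: the minimum of 30, split evenly, as the permuted blocks of 2, 4 or 6 suggest.
- The same variance at each visit, set to 1.
- Within-child correlation ρ from 0.5 to 0.8. Step 4 extends this to 0.9.

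**3. Baseline adjustment, no extra visits**

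Per-child variance is 2(1 − ρ) for the change score and 1 − ρ² for 12-month FEV1 adjusted for baseline. The ratio is (1 + ρ)/2.

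| ρ | Change score | Baseline-adjusted | Ratio |
|---|---|---|---|
| 0.5 | 1.00 | 0.75 | 75% |
| 0.7 | 0.60 | 0.51 | 85% |
| 0.8 | 0.40 | 0.36 | 90% |

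At ρ = 0.7 the approximate 95% half-width for the difference between arms falls from 1.96 × √(2 × 0.60/15) = 0.55 SD to 1.96 × √(2 × 0.51/15) = 0.51 SD. These are large-sample formulas. Estimating the baseline slope from 30 children costs a factor of about 1 + 1/(30 − 4) = 1.04, which moves the range to about 78% to 93%.

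**4. Interim values, 12-month contrast**

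The comparison is a baseline-adjusted model with visits at 0 and 12 months against one with visits at 0, 3, 6 and 12 months, with a separate treatment effect at each follow-up visit.

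- Complete data: at ρ = 0.7 the variance of the 12-month difference is 2 × 0.51/15 = 0.068 in both models. The reduction is 0% at every ρ tried (0.5, 0.7, 0.8, 0.9).
- 20% missing at 12 months (3 of 15 per arm, assumed): at ρ = 0.7 the variance falls from 0.0850 to 0.0809 with equal correlation between visits (4.8%), or to 0.0780 with correlation that decays over time (8.2%). Over ρ from 0.5 to 0.9 the reductions are 3.3% to 6.1% and 6.7% to 9.5% respectively.

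**5. Interim values, average over follow-up**

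Under equal correlation, the mean of three follow-up values adjusted for baseline has variance (1 + 2ρ)/3 − ρ².

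- ρ = 0.5: 0.417 against 1.00, or 42% of the change-score variance.
- ρ = 0.7: 0.31 against 0.60, or 52%.
- ρ = 0.8: 0.227 against 0.40, or 57%.

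Two separate changes are mixed here. At ρ = 0.7, the step from 0.60 to 0.51 is baseline adjustment. The step from 0.51 to 0.31 comes from replacing the 12-month difference with the average over 3, 6 and 12 months, which is a different estimand.

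**The case against.** The strongest reply is that row 4 is a bundle. Its marks at 3, 6 and 12 months are explained by the EPIC download and the follow-up questionnaire, which do occur at those visits. With no baseline column, the table is plainly not an item-by-visit schedule, while the timeline and the FEV1 analysis agree. On this view the table is loosely drawn and no 3- or 6-month FEV1 analysis was intended. That is plausible, and it limits the point to a reconciliation. It does not remove it: rows 2 and 3 of the same table leave the 6-month cell blank, so the table does distinguish time points elsewhere.

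A reader might also infer three stronger things that the documents do not support.

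- **That routine clinic values are being discarded.** Quarterly clinics and usual-care spirometry make such values likely. But the Spirometry text describes how the test is done, not how often, and nothing says it is done at every clinic visit.
- **That the two-point plan wastes about half the available precision.** The 42% to 57% figure belongs to the average over follow-up. It does not apply to the planned 12-month change.
- **That two points cannot address change over time.** An entry-to-12-month change compared between arms is a change over time, and the objective promises no trajectory.

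Finally, the choice of model is often left to the SAP, which is not at hand. However, the Protocol does not leave it open: it names an unadjusted comparison of change scores.

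**Conclusion.** The point holds in a limited form. The objectives table contradicts the timeline and questionnaire text for both FEV1 and quality of life. The unadjusted FEV1 change score can be improved with data already collected: baseline adjustment alone leaves 75% to 90% of its variance at ρ from 0.5 to 0.8 (about 78% to 93% after the small-sample cost), with no extra visits.

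Interim FEV1 is worth having mainly so that a child without a 12-month value still contributes. For the 12-month contrast its gain is nil with complete data and about 3% to 10% with 20% missing. The correlations, the missing fraction and the even split are assumptions, not Protocol figures. Severity is low: these are secondary outcomes in a pilot with no power claim.

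**What to change.** 1. Make the objectives table, timeline, questionnaire text and section 6 agree on the visits for FEV1 and for CFQ-R and EQ-5D-Y. Splitting row 4 by outcome would do it. The cost is a wording change.
2. Replace the unadjusted change-score comparison with a model for 12-month percent predicted FEV1, adjusted for baseline FEV1 and the two-level risk stratum used in randomisation. This needs no new data.
3. State whether routine 3- and 6-month spirometry is in EPIC for both arms. If it is, extract the value from the nearest scheduled quarterly visit by the same rule in each arm, and exclude the exacerbation-triggered tests that only the intervention arm receives. Analyse with a repeated-measures model and report the 12-month contrast. If the average over follow-up is also reported, label it as a separate estimand.

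Step 3 costs up to two record extractions per child, or about 60 for 30 children. Its downsides are variable visit timing and some missing interim values. If routine values are not available in both arms, steps 1 and 2 are sufficient.
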